- History of biliary diversion
- Known positivity for Human Immunodeficiency Virus infection
- Active, serious medical disease with likely life expectancy less than 5 years
- Active substance abuse including inhaled or injected drugs, in the year prior to screening
- Pregnancy, planned pregnancy, potential for pregnancy and unwillingness to use effective birth control during the trial, breast feeding
- Participation in an IND trial in the 30 days prior to randomization
- Any other condition which, in the opinion of the investigator, would impede compliance or hinder completion of the study
- Failure to give informed consent

Outcome measures

Primary:

Centrally scored histological improvement in NAFLD from baseline to the end of 72 weeks of treatment, where improvement is defined as:

- (1) No worsening in fibrosis; and
- (2) A decrease in NAFLD Activity Score (NAS) of at least 2 points

65 weeks from 1st patient randomized:

Change in serum ALT from baseline to 24 weeks
Adverse events and other safety measures through interim analysis

Secondary changes in the following from baseline to 72 weeks:

NASH diagnosis (from definite or indeterminate NASH to not-NASH)
Fibrosis score
Hepatocellular ballooning score
Each component score in the NAS
Change in serum aminotransferase and gamma-glutamyl transpeptidase (GGT) levels
Change in MRI-determined hepatic fat
Change in fasting markers of insulin resistance (HOMA, adipo-IR index)
Change in post-glucose parameters of insulin (2-hour glucose and fatty acids)
Change in anthropometric measurements (weight, BMI, waist to hip ratio, waist circumference)
Change in bile acid levels
Change in cytokeratin 18 (CK-18) fragment assay
Change in fibroblast growth factor (FGF-19) levels
Change in markers of hepatic apoptosis, inflammation, and fibrosis
Change in health related quality of life (HR-QoL) scores

Screening and enrollment

Up to 16 weeks screening prior to randomization
72-week treatment period
24-week post-treatment washout period
Length of recruitment: 78 weeks (18 months)
Expected enrollment rate: 35 patients each center (~2 patients per month at each center)

Number of clinical centers: 8

Visit schedule:

Screening period can last no more than 16 weeks (112 days) after registration
Randomization: final pre-treatment interview, dispensing of study drug

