A formal vanguard analysis, marking the end of the vanguard phase of the FLINT trial, will be performed approximately 65 weeks after the first patient is randomized. The analysis will be focused on interim efficacy outcomes and safety information using data from the estimated 25-40% of patients who will have completed at least 24 weeks of follow-up by the time of the interim analysis. Our pre-specified interim criterion for efficacy for continuing the FLINT trial beyond the vanguard phase is based on serum ALT: the criterion for continuation will be considered met if the upper 95% confidence limit on the between-group mean difference in mean changes from baseline to the 24 week measure of ALT, comparing the obeticholic acid versus placebo groups, is at least a 20% net reduction in serum ALT from the overall baseline mean ALT. The analysis will also include detailed safety data, as required by the DSMB, to determine whether any emergent safety issues are present. This vanguard safety analysis will consist of, but is not limited to, counts of adverse events (AEs) and serious adverse events (SAEs) by treatment group with associated P-values based on Fisher's exact tests or other tests, as appropriate. The final decision as to whether to continue the FLINT trial beyond the vanguard phase will be made by the NIDDK program official for the NASH CRN trial, which will be informed by any recommendations from the FLINT DSMB, taking the interim criterion for efficacy, safety, and other relevant information that may arise into account.

Interim analysis

The DSMB will review one planned interim analysis of the primary histological outcome measure. O'Brien-Fleming statistical stopping guidelines for efficacy will be applied. This interim efficacy analysis will occur when approximately 50% (140 of the 280 patients) have completed both baseline and 72 week biopsies. Based on the Lan-DeMets method for group sequential trials using O'Brien-Fleming boundaries (Reboussin et al., 2000), the levels of significance for the interim and final analyses will be $\alpha=0.00305$ and $\alpha=0.049$, respectively.

Sample size considerations

- Total of 280 patients in 2 groups of equal size (140 per group)
- Primary comparison: Obeticholic acid group vs. Placebo group
- Primary outcome measure: Histological improvement in NAFLD (defined above)
- Error protection: Type I = 0.05 and Type II = 0.10 (90% power)

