3.3 Vanguard analysis

Rationale

In order to safeguard the interests of the patients against futility, unnecessary liver biopsies, and adverse events attributable to the study drug, the FLINT trial utilizes a vanguard study design. This is needed because there are no human data on the efficacy and safety of obeticholic acid as a treatment for NASH. The vanguard design is one that allows interim data analysis with a decision regarding trial design or continuation based on the results of this analysis.

Timing

The vanguard analysis will be performed 65 weeks after the enrollment of the first subject. We anticipate that approximately 25-40% of subjects will have completed 24 weeks of treatment with either placebo or obeticholic acid by this time.

Measures

ALT measurement at 24 week visit (window: 18-30 weeks after randomization).

Analysis

The interim ALT target will be considered met if the upper 95% confidence limit includes a 20% net reduction in serum ALT from baseline to 24 weeks comparing the obeticholic acid versus placebo groups.

Study continuation or discontinuation

After analysis of the interim vanguard data by the DCC, the results of the analysis will be presented and discussed during a meeting of the DSMB attended by the DSMB, DCC, and NIDDK. Shortly thereafter, the results of the analysis and the recommendations of the DSMB will be discussed on a conference call attended by the DCC, NIDDK staff, and industry partner. The final decision to continue or stop the study will be made by the NIDDK program official for the NASH CRN in consultation with the Data Coordinating Center, the DSMB, and the industry partner. This decision will be reached before any follow-up biopsies are obtained. The NASH CRN investigators will not be told the results of the analysis unless the decision has been made to discontinue the trial. If the NIDDK Program Official determines that the trial should be continued, only the decision to continue will be communicated; the investigators will not be told any details or results of the interim vanguard analysis. No study completion liver biopsies are to be performed until the decision has been made to continue the study.

Site notification of study termination

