5.4 Follow-up visits

Patients will return for follow-up visits at 2, 4, 12, 24, 36, 48, 60, 72, and 96 weeks after randomization. Each visit will have an interval of time surrounding the ideal date for the visit during which the visit may be done and the data included in the trial database. The ideal target date for a visit is the exact anniversary from randomization. Visit windows will be constructed to be contiguous, so that at any point in time, a follow-up visit window is open. The specific procedures to be completed at each of the follow-up visits are described below.

Week 2 and 4 visits

Follow-up medical history including review of medications, adverse events and study drug compliance, and interim alcohol consumption. These two visits may be conducted by telephone interview. Remind patient not to take study medication on the day of the week 12 visit until the visit has been completed.

Week 12 visit

Follow-up medical history including review of medications, adverse events, and interim alcohol

consumption; focused physical examination, including height, weight, and vital signs (blood pressure, heart rate, respiratory rate, and body temperature). Draw blood for laboratory testing (hepatic panel (total bilirubin, direct bilirubin, AST, ALT, alkaline phosphatase, GGT), fasting lipid profile (total cholesterol, triglyceride, LDL, HDL), and fasting glucose and insulin). Draw 10 mL of blood for serum and 10 mL of blood for plasma banking (including measurements for free fatty acids, bile acids, FGF-19 and CK-18) at the NIDDK Biosample Repository. Women of childbearing potential must have a negative pregnancy test to continue on study drug. Dispense study drug and review study drug adherence with patient. Remind patient not to take study medication on the day of the week 24 visit until the visit has been completed.

Week 24 visit

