7.5 Vanguard analysis

An unmasked vanguard analysis, using change in ALT (U/L) from baseline to the 24 week follow-up visit as the primary vanguard outcome, will be carried out for review by the DSMB in order to advise the NIDDK on whether the FLINT trial should continue. The vanguard design requires that the vanguard analysis and the decision to continue must be completed before any patient undergoes a 72 week end-of-study biopsy. This means that the vanguard analysis of ALT change must occur approximately 65 weeks after the first randomized patient is enrolled when between 70 (25% of total sample size) and 112 (40%) will have a 24 week ALT measure, but before the first patient (or any other patient) has undergone a 72 week liver biopsy.

The vanguard analysis statistical guideline indicating sufficient evidence that, compared to placebo, 24 weeks of treatment with obeticholic acid results in a greater reduction in ALT (BL – 24 weeks) will be considered met if the upper 95% confidence limit for the net percentage reduction in mean ALT (BL-24 weeks) in the obeticholic acid group vs. placebo group is greater than or equal to 20%. The net reduction and 95% upper confidence interval will be calculated from a multiple linear regression model with patient level changes in ALT (U/L) at baseline minus ALT (U/L) at 24 weeks as the response variable (y) and independent variables: obeticholic acid indicator ($x_1=1$, if obeticholic acid, 0, if placebo) and baseline ALT (U/L) (x_2): $E(y_i)=\beta_0+ \beta_1x_1+ \beta_2x_2+\epsilon_i$, $i=1,2,\dots,n$; n =number of patients in the vanguard analysis and ϵ_i are i.i.d. Gaussian($0,\sigma^2$).

The estimated between group (obeticholic acid vs. placebo) difference in mean change in ALT from BL

to 24 weeks is b_2 with 95% CI: $b_2 \pm t_{n-3} \widehat{\sigma}(b_2)$ where t_{n-3} is the 97.5th percentile of the t-distribution with $n-3$ degrees of freedom and $\widehat{\sigma}(b_2)$ is the estimated standard error of b_2 from the regression analysis. The estimated net reduction in ALT in the obeticholic acid group, expressed as percentage of the overall baseline mean ALT, \overline{ALT} , is $100 \times b_2 / \overline{ALT}$ with upper 95% confidence limit: $100 \times [b_2 + t_{n-3} \widehat{\sigma}(b_2)] / \overline{ALT}$. SAS PROC REG will be used to fit the regression model and calculate the upper 95% confidence limit to determine whether its value is a 20% or more net reduction in ALT.

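### The vanguard ALT criterion leaves out week-12 ALT values already collected in patients without a week-24 value: a modest, cheaply recovered loss of precision, not an error

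*Protocol*

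**What the plan says.** The vanguard part of the protocol synopsis bases the interim efficacy look on "data from the estimated 25-40% of patients who will have completed at least 24 weeks of follow-up". Section 7.5 sets the model: a linear regression in SAS PROC REG with "patient level changes in ALT (U/L) at baseline minus ALT (U/L) at 24 weeks as the response variable", and treatment and baseline ALT as the only covariates. The limit uses n-3 degrees of freedom and is divided by the overall baseline mean ALT. The criterion is met when the upper 95% limit for the net reduction is 20% or more. (Section 7.5 calls the treatment estimate b2 although the treatment indicator is x1; I read it as the treatment coefficient.)

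On timing, section 3.3 says: "The vanguard analysis will be performed 65 weeks after the enrollment of the first subject". It defines the measure as "ALT measurement at 24 week visit (window: 18-30 weeks after randomization"). Section 7.5 expects the analysis to fall "when between 70 (25% of total sample size) and 112 (40%) will have a 24 week ALT measure".

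The week 12 visit in section 5.4 includes: "Draw blood for laboratory testing (hepatic panel (total bilirubin, direct bilirubin, AST, ALT, alkaline phosphatase, GGT"). The schedule in Appendix 10.2 agrees. Neither the synopsis nor sections 3.3, 7.5 or 7.6 bring that value into the ALT criterion. The mixed models in section 7.3 are sensitivity analyses for use when more than 10% of data are missing; they do not alter this rule.

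**The concern.** Any patient who has passed week 12 but has no ALT in the week-24 window drops out of the ALT test, although a baseline and an on-treatment ALT are already held. If the two on-treatment values are correlated given baseline, the week-12 value carries information about week 24, and the confidence interval is wider than the collected data require.

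The direction matters. The criterion is met when the upper limit reaches 20%, so a wider interval makes it easier for an ineffective drug to meet it. Section 3.3 gives protection against futility and unnecessary liver biopsies as reasons for the vanguard design. Lost precision weakens that protection; it does not put an effective drug at risk.

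**Working it through.** **Inputs from the protocol**
- Synopsis, sample size: "Total of 280 patients in 2 groups of equal size (140 per group").
- Synopsis, recruitment: "Length of recruitment: 78 weeks (18 months").
- Analysis at week 65; 70 to 112 patients with a week-24 ALT (sections 3.3 and 7.5).

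**Assumptions not in the protocol**
- Visits fall on their nominal dates.
- Partial correlation ρ of week-12 and week-24 ALT given baseline: 0.5 to 0.8.
- Residual SD of ALT change: 50% of mean ALT, with 40% and 60% as alternatives.

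**1. The protocol's count.** 0.25 × 280 = 70 and 0.40 × 280 = 112, so the percentages are right. Uniform accrual does not give these counts: 280/78 = 3.59 per week, and 3.59 × (65 − 24) = 147 (53%). Using the ends of the 18-30 week window gives 3.59 × 47 = 169 or 3.59 × 35 = 126 (45%). All exceed 112, so the stated 25-40% implies slower early recruitment. The number of affected patients must therefore be given as a range.

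**2. Patients with week-12 but no week-24 ALT (m).** At nominal dates these were randomized between weeks 41 and 53.
- Constant rate matching the stated counts: 70/41 × 12 = 20; 112/41 × 12 = 33.
- Back-loaded accrual 280 × (t/78)^k, reaching 280 at week 78: k = 1.42 gives 112 at week 41 and m = 49; k = 2.16 gives 70 and m = 52.
- Uniform 280/78: 3.59 × 12 = 43, but paired with 147 at week 24.

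Patients randomized in the last 12 weeks (43 under uniform accrual) have neither value and are not recovered. Because the window opens at 18 weeks, some patients counted in m may already have a qualifying week-24 ALT.

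**3. Gain in precision.** With n patients at week 24, the variance of a likelihood-based repeated-measures estimate relative to the week-24-only regression is 1 − ρ² × m/(n + m). Under any constant rate m/(n + m) = 12/53 = 0.226, whatever n is.

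| Accrual | n, m | SE factor, ρ = 0.5 / 0.7 / 0.8 | SE reduction |
|---|---|---|---|
| Constant | 70, 20; 112, 33; 147, 43 | 0.971 / 0.943 / 0.925 | 3-7.5% |
| Back-loaded | 112, 49 | 0.961 / 0.922 / 0.897 | 4-10% |
| Back-loaded | 70, 52 | 0.945 / 0.889 / 0.853 | 5.5-15% |

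Simulation agrees closely: for n = 70, m = 20 the simulated factors were 0.974 / 0.949 / 0.929.

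**4. Effect on the criterion.** SE = 2 × SD/√n, in percentage points of mean ALT. P(met) = P(Z ≥ (20 − true effect)/SE − t). Take n = 112, SD 50% and t = 1.982.
- Present regression: SE = 100/√112 = 9.45. With no true effect, 20/9.45 − 1.982 = 0.134, so P = 45%.
- Constant accrual, ρ = 0.5: SE = 9.18, P = 42%. With ρ = 0.8: SE = 8.74, P = 38%.
- SD 40%: 25% falls to 19-23%. SD 60%: 59% falls to 53-57%.
- n = 70, SD 50%: 63% falls to 57-61% (constant accrual) or 51-59% (back-loaded).
- True 20% net reduction: the estimate is centred on the threshold, so about 97.5% pass whatever the SE.

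**The case against.** The strongest reply is that nothing is stated wrongly. A baseline-adjusted regression at the pre-specified visit is a valid analysis of the stated outcome. Patients not yet at week 24 are missing because of the calendar, so omitting them does not bias the estimate. That stands, and it sets the weight of the point.

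The gain also rests on a correlation and an SD that the protocol does not give. Section 2.5 says that ALT improved over 3-6 months on pioglitazone and vitamin E. That describes mean response to other drugs, not within-patient correlation on obeticholic acid. This stands too, which is why ranges are shown.

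A reader might infer more than the text supports:
- **That every enrolled patient has a week-12 ALT.** Recent enrollees and those lost before week 12 do not.
- **That every early dropout is excluded and biases the result.** Section 5.10 keeps patients who stop drug for side effects in follow-up, so they can supply a week-24 ALT. The only missing-data figure is at most 10% by week 72, expected to be balanced (section 7.3). Bias from differential loss by week 24 is possible, but nothing in the protocol sizes it.
- **That excluded patients count for nothing.** This is true of the ALT test only; the safety counts are not limited to patients with a week-24 ALT.
- **That this test alone decides continuation.** The NIDDK program official decides, weighing the DSMB's recommendations, safety and other information. The criterion is a guideline.

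**Conclusion.** The point holds as a loss of efficiency. Collected week-12 ALT is unused, and using it would narrow the limit by about 3-7.5% under constant accrual and by up to about 15% if accrual is back-loaded, for ρ between 0.5 and 0.8. In the example with 112 patients and an SD of 50%, the chance that a no-effect drug passes drops by about 2 to 7 percentage points, with no loss for a drug that truly reaches 20%.

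It would be wrong to conclude that the missing week-12 data explain the leniency of the criterion. A no-effect drug would still pass 38-42% of the time in that example. That comes from asking only whether the upper limit reaches 20%, which this change leaves alone. I rate it a cheap improvement, optional in priority.

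**What to change.** In section 7.5, estimate the week-24 treatment contrast from a likelihood-based repeated-measures model, for example in SAS PROC MIXED:
- responses: ALT change at weeks 12 and 24;
- terms: treatment, visit, treatment-by-visit and baseline ALT-by-visit;
- unstructured covariance;
- all randomized patients with at least one of the two values.

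Compare the limit of the week-24 contrast, divided by the overall baseline mean ALT, with the unchanged 20% criterion. State the degrees-of-freedom method, since n-3 no longer applies. Keep the present regression as a check, and align the synopsis wording for ALT.

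The cost is a few lines of text and a different procedure, with no new visits, samples or patients. The downside is a slightly more complex model that assumes the absent week-24 values are missing at random. That is reasonable for patients not yet due, and for those lost after week 12 it is weaker than what the completers-only analysis needs.

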1.1 Primary hypothesis

Administration of the farnesoid X receptor (FXR) ligand obeticholic acid (OCA) for 72 weeks to subjects with biopsy evidence of nonalcoholic steatohepatitis (NASH) will result in improvement in their liver disease as measured by changes in the NAFLD activity score (NAS).

1.2 Principal objective

To evaluate whether treatment with obeticholic acid, 25 mg daily for 72 weeks compared to treatment with placebo, improves the severity of NAFLD as determined from hepatic histology.

2. Background and significance

2.1 Introduction

NASH has become the most common form of chronic liver disease in the developed world. It commonly occurs in the setting of obesity, insulin resistance, and a sedentary lifestyle, and it is often considered to be the liver manifestation of the metabolic syndrome. The primary form of treatment is lifestyle modification with changes focused on dietary and exercise habits. Unfortunately, achieving and maintaining these changes is difficult or impossible for many individuals. Pharmacologic treatments have been sought but none has proved universally efficacious. This may be related to the fact that the histopathological changes seen on liver biopsy currently described as NASH may be the result of multiple pathogenetic mechanisms acting in concert to varying degrees. Based on the prevalence and risk of progression of NASH to cirrhosis and cancer, the burden of significant disease is large and drug therapy to prevent or treat NASH is needed.

2.2 Definitions

Nonalcoholic fatty liver disease (NAFLD) is defined by the presence of greater than "normal" amounts of fat in the liver. The pathologists' definition is based on observed steatotic droplets (triglyceride) exceeding 5% of surface area. This definition evolved from older studies showing that the normal liver was 5% lipid. Properly performed, magnetic resonance imaging and spectroscopy can accurately quantify liver triglyceride content non-invasively. Based on a population study, an MR spectroscopy-determined 5.5% fat fraction has been suggested as a classification threshold for non-invasively differentiating individuals with NAFLD from those without fatty liver.¹ How well the histological and MR spectroscopy-based classification thresholds correlate with each other has not been determined.

Nonalcoholic steatohepatitis (NASH) is the name applied to a constellation of biopsy abnormalities occurring in the presence of NAFLD that typically includes hepatocyte ballooning with or without Mallory-Denk bodies, a mixed polymorphonuclear leukocyte and mononuclear inflammatory cell infiltrate in the lobules, chronic inflammation in the portal tracts and sometimes Rappaport zone 3 perisinusoidal fibrosis.²

A name for **NAFLD that is not NASH** has not been universally established. Terms such as nonalcoholic fatty liver (NAFL), simple steatosis, benign steatosis, bland steatosis, and isolated steatosis have been used, but each has limitations that preclude general acceptance.³

2.3 Significance of NASH

Prevalence

Estimates of the prevalence of NAFLD in adults range from 17% to 46%.⁴⁻⁷ NASH has been found in 3-13% of adults, with its prevalence approaching 50% in patients with severe obesity and diabetes.^{6, 8-10}

Progression to cirrhosis

Approximately 20-40% of patients with NASH have some degree of fibrosis on their initial diagnostic liver biopsy, and thus have the potential to progress to cirrhosis. There is scant longitudinal data on how many patients with NASH will go on to develop cirrhosis. However, NASH cirrhosis and cryptogenic cirrhosis (most of which represents prior NASH) account for 10-12% of liver transplants. This figure probably underrepresents the relative likelihood of NASH progressing to cirrhosis compared to other forms of liver disease because many patients with NASH cirrhosis are not candidates for liver transplantation because of concomitant cardiovascular disease or severe obesity. Liver disease is the third most common cause of death in patients with NASH, behind cardiovascular disease and cancer.¹¹

Development of hepatocellular carcinoma

Hepatocellular carcinoma occurs in 2-4% of patients with NASH cirrhosis, roughly at the same rate as in patients with chronic hepatitis C.^{12, 13} Occasionally, patients with NASH but without cirrhosis present with hepatocellular carcinoma as well.¹⁴

Comorbidities

NASH is often found in patients with features of the metabolic syndrome including centripetal obesity, hyperlipidemia, hypertension, and impaired fasting glucose or overt diabetes. Additional manifestations of insulin resistance such as polycystic ovarian syndrome and acanthosis nigricans are also found in association with NASH. Although some authors have suggested that the liver can contribute to the components of the metabolic syndrome, emerging data support the viewpoint that the liver is likely the target of lipotoxic injury in these settings and not a cause of the associated comorbidities.¹⁵

